## 7. Statistical Analysis

### 7.1. Sample size calculation

Response to treatment with biologics is estimated at 50%, meaning that half of included patients are expected to be non-responders. Considering a minimal sample of 10 patients that present the event of interest per independent variable included in the logistic regression model and a maximum of 10 independent variables per model, a minimum estimated sample of 200 UC patients and 200 CD patients is required.

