#### **7.4. Assessment of the primary objective: Evaluate the impact of the co-morbidities profile in IBD patients on treatment response to biological therapy**

In order to determine the level of correlation between the co-morbidities profile and treatment response, adjusting for sociodemographic and clinical profile of patients, two logistic regression models will be conducted. The dependent variable of the models will be the lack of response during the induction phase (primary non response) and the loss of response during the maintenance phase (secondary loss of response) (see section 6.4.6). In both models independent variables will include all comorbidities included in the study, as well as sociodemographic and clinical variables as covariates. The maximum number of independent variables included in the model will be defined according to the number of patients per response category in the dependent variable. The maximum number of variables will be defined to ensure a minimum of 10 patients per independent variable and response category in the dependent one.

Depending on the volume of patients that have discontinued a biological treatment and started treatment with a different biologic during the reference period, this sample may be separately analyzed.

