## **7.6. Co-morbidities profile according to the level of IBD severity**

The percentage of patients reporting each co-morbidity at treatment initiation will be compared according to the IBD severity assessed using the PMS and the general disease activity for UC patients and the HBI and the general disease activity for CD patients. Multivariable regression models will be used to assess the relationship between the co-morbidities profile and the level of IBD severity.

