- Non severe (Remission <5; Mild disease 5-7; Moderate disease 8-16)
- Severe disease >16

Partial Mayo Index Score

- Non severe (Remission = 0-1; Mild Disease = 2-4; Moderate Disease = 5-7)
- Severe Disease =8-9

We will compare the percentage of patients reporting each co-morbidity between IBP severe or non-severe using Chi-Square.

A logistic regression analysis will be performed, in which **IBP severe or non-severe at baseline** will be used as the dependent variable and patient disease (CD or UC) and different comorbidities variables will be used as independent variables, yielding the following results: Odds Ratio, 95%CI, p-value, sensitivity and specificity.

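### Baseline severity is defined in four ordered bands but analysed only as severe versus the rest; the loss depends on a severity mix that the documents do not give

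*SAP*

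**What the plan says.** The third secondary objective (Protocol 5.2, SAP 3.5) is to determine the comorbidity profile according to the level of IBD severity. Protocol 7.6 bases severity on the PMS or HBI together with general disease activity, and adds: "Multivariable regression models will be used to assess the relationship between the co-morbidities profile and the level of IBD severity". It states no cut-point.

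SAP 7.3 gives four bands per index: remission, mild, moderate and severe. For Crohn's disease the non-severe group is "Non severe (Remission <5; Mild disease 5-7; Moderate disease 8-16", and severe is an HBI above 16. For ulcerative colitis a PMS of 0 to 7 is non-severe and 8 to 9 is severe. Each comorbidity is compared between the two groups by chi-square. One logistic model then pools both diseases, with disease and the comorbidity variables as predictors. The SAP's table index has only these two outputs for the objective (14.3.2.4 and 14.3.2.5), and both are binary.

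The only numerical standard for model size is in Protocol 7.1, for the response models: "a minimal sample of 10 patients that present the event of interest per independent variable", with "a maximum of 10 independent variables per model". Protocol 7.4 repeats the standard as a cap, under the primary objective.

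**The concern.** The split treats a patient in remission and a patient with an HBI of 16 as having the same outcome, and likewise a PMS of 0 and of 7. Any relation between comorbidity and severity across the lower three bands is invisible to both planned analyses. If few patients are severe, the logistic model also has few events for a predictor list that could reach 20 terms, with sparse cells and unstable odds ratios. At stake is whether this objective gets an interpretable answer. HBI and PMS at the start of the reference period are already to be collected (Protocol 6.4.4), so the information exists.

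**Working it through.** **Inputs from the documents.** Protocol 7.1: "a minimum estimated sample of 200 UC patients and 200 CD patients is required", so 400 pooled; 10 events per variable; at most 10 variables; 50% non-response. SAP 7.3: 19 yes/no comorbidities plus disease, up to 20 terms.

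**Input not in the documents.** The severe share at baseline. Assumed range: 5% to 30%.

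**1. The plan's own figure.** N = 10 × 10 / 0.50 = 200 per disease. This reproduces the stated sample size, which was derived for the response models. No such calculation is given for the severity model.

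**2. Events per predictor in the severity model.** Events = 400 × severe share; ratio = events / 20.

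| Severe share (assumed) | Events | Per predictor, 20 terms | Predictors allowed at 10 each |
|---|---|---|---|
| 5% | 20 | 1 | 2 |
| 10% | 40 | 2 | 4 |
| 20% | 80 | 4 | 8 |
| 30% | 120 | 6 | 12 |
| 50% | 200 | 10 | 20 |

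With all 20 terms, only an even split reaches 10. The list length therefore contributes to the shortfall as well as the cut. With 10 predictors the ratios at 5, 10, 20 and 30% would be 2, 4, 8 and 12.

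**3. Information kept by the split, against the four bands.** For a small effect, proportional-odds information is proportional to (1 − Σp_k³)/3 and binary information to p(1 − p), where p is the severe share. The ratio is 3p(1 − p)/(1 − Σp_k³). All mixes below are assumptions.

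| Remission / mild / moderate / severe (%) | 3p(1 − p) | 1 − Σp_k³ | Ratio |
|---|---|---|---|
| 5 / 20 / 70 / 5 | 0.1425 | 0.6488 | 0.22 |
| 5 / 20 / 65 / 10 | 0.27 | 0.7163 | 0.38 |
| 2 / 8 / 80 / 10 | 0.27 | 0.4865 | 0.56 |
| 10 / 30 / 40 / 20 | 0.48 | 0.9000 | 0.53 |
| 5 / 25 / 50 / 20 | 0.48 | 0.8513 | 0.56 |
| 2 / 8 / 70 / 20 | 0.48 | 0.6485 | 0.74 |
| 5 / 15 / 50 / 30 | 0.63 | 0.8445 | 0.75 |

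These mixes illustrate the loss and do not bound it. If every patient were moderate or severe, then 1 − p³ − (1 − p)³ = 3p(1 − p). The ratio would be 1, and the four bands would add nothing.

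**4. Against a continuous, normally distributed score.** The share kept is φ(z)²/[p(1 − p)], with z the cut-point: 22%, 34%, 49% and 58% at 5, 10, 20 and 30% severe.

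**The case against.** - **The severe share is unknown.** A reader might infer that the split discards most of the information. The documents do not support that as a general statement. Against the four bands, more than half is kept in every 20-30% mix above, and in one 10% mix. Protocol 4 describes biologics as used in moderate to severe Crohn's disease and acute severe colitis, which suggests few patients in the lower bands and a smaller loss. However, the inclusion criteria set no minimum activity. The objection stands as a limit on the size of the loss.

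- **Entry of all 19 comorbidities is not stated.** The primary model in SAP 7.2 says all comorbidities enter; the severity model is worded more loosely. Full entry is still the likely reading. The same loose wording precedes the extraintestinal manifestations in SAP 7.3, where all nine listed in SAP 5.3 are then named. The screening and stepwise steps in SAP 7.2 are not stated for this model. The figures of 1 to 6 remain conditional on this reading and on the assumed share.

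- **A reader might infer that the plan breaks its own rule of 10.** It does not, strictly. Protocol 7.1 and 7.4 write the rule for the response models, and nothing applies it to severity. Carried over, it would act as a cap on predictors. It is a benchmark here.

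- **A reader might infer that the SAP contradicts Protocol 7.6 on the form of the model.** Protocol 7.6 prescribes neither an ordinal nor a continuous outcome, and severe versus non-severe is a coarse level of severity. The split answers the objective thinly but does not contradict it.

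- **The alternative carries assumptions.** A pooled ordinal model treats HBI and PMS bands as comparable at every cut, and its gain shrinks if the association is confined to severe disease. This stands and belongs with the fix.

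**Conclusion.** The point holds in conditional form. The SAP defines four ordered bands, merges three, and offers no ordinal or continuous analysis of an objective about level of severity. Under the assumed mixes, the split keeps roughly 0.2 to 0.55 of the four-band information at 5-10% severe and roughly 0.55 to 0.75 at 20-30% severe. With 400 patients and 20 terms, events per predictor are 1, 2, 4 and 6 at 5, 10, 20 and 30% severe. The split and the uncapped list both contribute to those low ratios. Confidence is moderate, because the severity mix and the final predictor list are not in the documents. This is a secondary objective in a study that SAP 5.1 calls descriptive, so the point is a cheap improvement; it does not threaten the primary analysis.

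**What to change.** In SAP 7.3:

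- Make the four-level baseline band the dependent variable in a proportional-odds model, with disease as a covariate.
- Use a trend test across the bands for each comorbidity.
- Replace the 19 separate terms with the Charlson score, which SAP 5.3 already summarises, or with a short prespecified set of grouped comorbidities.
- Keep severe versus non-severe as a supportive table.

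The cost is SAP wording, one different model call and revised titles for tables 14.3.2.4 and 14.3.2.5. No new data are needed. The proportional-odds assumption and the pooling of HBI and PMS bands must be checked, for example by fitting each disease separately, at the price of 200 patients per fit. The gain will be small if nearly all patients prove to be moderate or severe.

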7.3. Secondary efficacy endpoints

- Secondary endpoint: Evaluate the impact of Extraintestinal Manifestations profile in IBD patients on treatment response to biological therapy.

The analysis that will be performed to answer the objective will be the following:

To evaluate the impact of extraintestinal manifestations profile in IBD patients on treatment response to biological therapy, a logistic regression analysis will be performed, in which **lack of response during the induction phase** will be used as the dependent variable and patient disease (CD or UC) and different extraintestinal manifestations variables (arthropathy and arthritis, metabolic bone disease, eye disease, oral, aural and nasal disease, skin disease, hepato-pancreato-biliary disease, neurological disease, cardiovascular manifestations of IBD,

pulmonary manifestations of IBD) will be used as independent variables, yielding the following results: Odds Ratio, 95%CI, p-value, sensitivity and specificity.

We will repeat this analysis with the **loss of response during the maintenance phase variable** as dependent variable.

- **Secondary endpoint: Describe the percentage of IBD patients exhibiting co-morbidities.**

The analysis that will be performed to answer the objective will be the following:

We will provide the frequencies, percentages and 95%CI of the following comorbidities for patients with Crohn's Disease and Ulcerative Colitis separately:

- Myocardial Infarction (yes/no).
- Congestive Heart Failure (yes/no).
- Peripheral Vascular Disease (yes/no).
- Cerebrovascular Disease (yes/no).
- Dementia (yes/no).
- Chronic Obstructive Pulmonary Disease (yes/no).
- Connective Tissue Disease (yes/no).
- Peptic Ulcer Disease (yes/no).
- Mild Chronic Hepatopathy (yes/no).
- Diabetes Mellitus (yes/no).
- Hemiplegic (yes/no).
- Moderate-Severe Chronic Kidney Disease (yes/no).
- Diabetes with lesions in target organs (yes/no).
- Solid Tumor (yes/no).
- Leukemia (yes/no).
- Lymphoma (yes/no).
- Moderate-Severe Chronic Hepatopathy (yes/no).
- Solid tumor with metastases (yes/no)
- Acquired immunodeficiency syndrome (AIDS) (yes/no).

- **Secondary endpoint: Determine the co-morbidities profile according to the level of IBD severity.**

The analysis that will be performed to answer the objective will be the following:

We will classify the patients into IBD severe or non-severe at baseline based on the HBI and PMI scores according the following criteria:

Harvey-Bradshaw Index score

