14.3 EFFICACY DATA			
14.3.1 Primary efficacy parameter			
14.3.1.1 Comparison of subjects presenting comorbidities, sociodemographic and clinical variables based on the lack of response during the induction phase (primary response vs primary non-response)	COMP1 / COMP4	Study population	
14.3.1.2 Logistic regression: Lack of response during the induction phase	RL	Study population	
14.3.1.3 Comparison of subjects presenting comorbidities, sociodemographic and clinical variables based on the loss of response during the maintenance phase (primary response maintenance vs loss of response)	COMP1 / COMP4	Study population	
14.3.1.4 Logistic regression: Loss of response during the maintenance phase	RL	Study population	

TITLE	TABLE TYPE	ANALYSIS SET	COMMENT
14.3.2	Secondary efficacy parameters		
14.3.2.1	Logistic regression: Lack of response during the induction phase based on the extraintestinal manifestations	RL	Study population
14.3.2.2	Logistic regression: Loss of response during the maintenance phase based on the extraintestinal manifestations	RL	Study population
14.3.2.3	Comorbidities description according to IBD	CAT2	Study population
14.3.2.4	Comparations of comorbidities between IBD severe vs non-severe at baseline	COMP1	Study population
14.3.2.5	Logistic regression: IBD severe or non-severe at baseline based on the comorbidities and patient disease	RL	Study population

TYPES OF TABLES

Examples for descriptive analysis of categorical variables:

CAT2

		Variable 2						
		Value a		Value b		...		
Variable 1	Value a	N	%	N	%	N	%	Total
	Value b							
	...							
	Total							

Examples for descriptive analysis of continuous variables:

CONT2

			Variable 1			
			N	Mean	Median	Standard deviation
Variable 2	Value a					Minimu
	Value b					m
	...					

Examples for multivariable analysis or comparations:

Chi-square results

COMP1

	Value	df	Asym. Sig. (2-sided)	Exact Sig. (2-sided)	Exact Sig. (1-sided)
Pearson Chi-square					
Continuity correction					
Likelihood Ratio					
Fisher's Exact Test					
Linear by linear association					
N of valid cases					

T-test results

COMP 4

Independent Samples Test

			Variable	
			Equal variances assumed	Equal variances not assumed
Levene's Test for Equality of variances	F			
t-test for Equality of means	t			
	df			
	Sig. (2-tailed)			
	Mean Difference			
	Std. Error Difference			
	95% Confidence Interval of the difference		Lower	Upper

Logistic regression results

LR

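### The comorbidity-by-severity table (SAP 7.3, Table 14.3.2.4) pools Crohn's disease and ulcerative colitis in an unstratified chi-square, so a difference between the diseases can look like a severity effect; the adjusted model beside it is not affected

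*SAP*

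**What the plan says.** Protocol 7.6 names a severity measure for each disease: "IBD severity assessed using the PMS and the general disease activity for UC patients and the HBI and the general disease activity for CD patients". For the relationship itself it turns to modelling: "Multivariable regression models will be used to assess the relationship between the co-morbidities profile and the level of IBD severity".

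SAP 7.3, third secondary endpoint, builds one binary variable: "We will classify the patients into IBD severe or non-severe at baseline based on the HBI and PMI scores according the following criteria". For CD the cut-off is "Severe disease >16" on the HBI. For UC it is "Severe Disease =8-9" on the partial Mayo score. Two analyses of that variable follow:

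- a univariate comparison, "We will compare the percentage of patients reporting each co-morbidity between IBP severe or non-severe using Chi-Square", reported in SAP Appendix 1, Table 14.3.2.4, under the title "Comparations of comorbidities between IBD severe vs non-severe at baseline";
- a logistic regression of severe v non-severe on disease (CD or UC) and the comorbidities, reported in Table 14.3.2.5.

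The SAP does ask for results by disease in three places: section 5.1 (subject description), section 6 (treatment description) and, within 7.3, the prevalence endpoint. None of these covers the severity comparison. Elsewhere in section 7, disease is a candidate variable or a model covariate, so those analyses pool CD and UC. The natural reading is that the chi-square is pooled too.

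**The concern.** The label severe comes from two different scales with two different cut-offs. Nothing in the documents suggests that an HBI above 16 and a partial Mayo score of 8-9 select similar shares of patients, so disease itself partly decides who falls in the severe column. If a comorbidity is also more common in one disease than in the other, the pooled two-by-two table shows an association that exists in neither.

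Table 14.3.2.4 is the only planned comparison of comorbidity percentages by severity. A significant row could mean only that one disease is over-represented among the severe. The bias can also run the other way and hide a real association. Either way, the row may disagree with the adjusted result in the next table, and a reader who takes the simpler table would be misled.

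**Working it through.** **The plan's own figure.** Protocol 7.1 allows 10 events per variable, at most 10 variables and a 50% event rate: 10 × 10 / 0.50 = 200 patients per disease. This reproduces the stated 200 UC and 200 CD. It is the only design figure in the plan and is not specific to the severity analysis.

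**Inputs.** n = 200 per disease (Protocol 7.1). The severe shares, the comorbidity prevalences and the two-sided 5% level are assumptions; the documents give none of them for this comparison. Within each disease, comorbidity and severity are taken as independent, so any pooled association is spurious.

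**Expected pooled table.** Let s be the severe share and c the comorbidity prevalence in each disease. With equal group sizes:

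- comorbidity among severe = (s_CD·c_CD + s_UC·c_UC) / (s_CD + s_UC)
- comorbidity among non-severe = [(1−s_CD)·c_CD + (1−s_UC)·c_UC] / (2 − s_CD − s_UC)

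Mild case, severe 10% v 20%, comorbidity 5% v 10%:
- severe: 20 + 40 = 60 patients, of whom 1 + 4 = 5 have the comorbidity (8.3%)
- non-severe: 180 + 160 = 340, of whom 9 + 16 = 25 (7.4%)
- pooled OR = (5 × 315) / (55 × 25) = 1.15

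Strong case, severe 5% v 40%, comorbidity 5% v 15%:
- severe: 10 + 80 = 90, of whom 0.5 + 12 = 12.5 (13.9%)
- non-severe: 190 + 120 = 310, of whom 9.5 + 18 = 27.5 (8.9%)
- pooled OR = (12.5 × 282.5) / (77.5 × 27.5) = 1.66

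The true odds ratio within each disease is 1 in both cases.

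**False-positive rates.** These come from simulated data sets (at least 40,000 per row). Each was tested with the pooled Pearson chi-square and with a Cochran-Mantel-Haenszel (CMH) test stratified by disease. The CMH statistic is (Σa − Σe)² / Σv. For each disease, a is the number of severe patients with the comorbidity, S the number severe, m the number with the comorbidity, e = S·m/n and v = S(n−S)m(n−m) / [n²(n−1)].

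| Severe, CD v UC | Comorbidity, CD v UC | Pooled OR | Pooled chi-square | Stratified CMH |
|---|---|---|---|---|
| 10% v 20% | 5% v 10% | 1.15 | about 7% | about 5% |
| 5% v 20% | 5% v 10% | 1.26 | 9% | about 5% |
| 5% v 30% | 5% v 10% | 1.34 | 12% | about 5% |
| 5% v 30% | 4% v 12% | 1.53 | 19% | about 5% |
| 5% v 40% | 5% v 15% | 1.66 | 30% | about 5% |
| 5% v 30% | 15% v 5% | 0.57 | about 15% | about 5% |
| 20% v 20% | 5% v 10% | 1.00 | 5% | about 5% |
| 5% v 25% | 5% v 5% | 1.00 | 4% | about 4% |

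The last two rows show that the bias vanishes when either rate is equal in the two diseases. The 15% v 5% row shows that it can reverse direction.

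**The case against.** The strongest reply is that the SAP already deals with this. The logistic regression that directly follows uses the same outcome and includes disease, and Protocol 7.6 assigns the relationship to multivariable regression. A crude table followed by an adjusted model is an ordinary layout. This stands, and it confines the defect to Table 14.3.2.4. A reader might infer that the whole secondary objective is answered by a confounded analysis; the documents do not support that.

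A reader might also infer that the SAP breaks a protocol rule to test CD and UC separately. Protocol 7.6 names a measure for each disease but does not say that the comparisons are run separately, and the objective is worded for IBD patients as a whole. Separate comparison is a reasonable reading of 7.6, not an instruction in it.

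The size is conditional. Larger inflation needs wide differences between the diseases on both rates. With severe 10% v 20% and comorbidity 3% v 5%, the pooled rate is about 5%. The output shell for this table also prints Fisher's exact test. That test rejects in 3-5% of runs when the differences are modest or the condition is rare, but it does not remove the confounding: in the 9% to 30% rows above it still rejects in 7-26%.

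Finally, significance tests within each disease would be a poor remedy. With 5% of 200 CD patients severe (10 patients) and a 5% comorbidity, the expected cell is 0.5, and the SAP lists 19 comorbidities. This stands too, and the fix below avoids it.

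**Conclusion.** The point holds for the univariate comparison only. As written, it pools two diseases whose severity is defined on different scales, with nothing to remove the effect of disease. The pooled false-positive rate is about 7% under mild assumed differences and 30% under large ones, against about 5% for a test stratified by disease. It is unbiased if CD and UC share either the severe share or the comorbidity prevalence. The actual size cannot be known from the documents, which give neither rate, so the upper figure is not a forecast.

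The endpoint is secondary and SAP 5.1 calls the methodology primarily exploratory, so the consequence is limited: a table that can mislead next to a model that adjusts for disease. The change is still worth making, because it is nearly free and takes a potentially confounded p-value out of the report.

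**What to change.** In SAP 7.3 and Table 14.3.2.4, replace the pooled chi-square with a Cochran-Mantel-Haenszel test and common odds ratio stratified by disease, using the exact version where cells are sparse. In the same table, show the counts and percentages of each comorbidity by severity within CD and within UC, as description only, without separate within-disease significance tests. Leave the logistic model in Table 14.3.2.5 as it is for this purpose.

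Appendix 1 already allows tables to be split during programming, so the display needs little formal change. The change of test should be written into 7.3 so that it is pre-specified. The cost is a sentence in the SAP, an extra set of columns and some sparse within-disease cells. No new data are needed.

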APPENDIX 1: INDEX OF SECTION 14 FOR THE CLINICAL REPORT

The following proposal for section 14 is done according to the pre-defined ICH-format. Minor changes from this planned index do not need to be amended in the SAP.

Comments in **Italics** will not be printed in table headers or footers.

Formal organization of tabulations may be changed during programming if appropriate, e.g., tables for the different variables may be combined into a single table, or tables with more than one variable may be split into several tables.

	TITLE	TABLE TYPE	ANALYSIS SET	COMMENT
14.	TABLES, FIGURES AND GRAPHS REFERRED TO BUT NOT INCLUDED IN THE TEXT			
14.1	DEMOGRAPHIC AND BASELINE DATA			
14.1.1	Subject disposition	CAT2	General population	
14.1.2	Subject characteristics			
14.1.2.1	Gender, Race	CAT2	Study population	
14.1.2.2	Level of education	CAT2	Study population	
14.1.2.3	Working status	CAT2	Study population	
14.1.2.4	Smoking habits / Alcohol abuse	CAT2	Study population	
14.1.3	Disease characteristics			
14.1.3.1	Time from diagnostic of disease	CONT2	Study population	
14.1.3.2	Charlson index	CONT2	Study population	

TITLE		TABLE TYPE	ANALYSIS SET	COMMENT
14.1.3.3 Disease location		CAT2	Study population	
14.1.3.4 Disease behavior		CAT2	Study population	
14.1.3.5 Extraintestinal manifestations		CAT2	Study population	
